## 1.2. Study Objectives and Endpoints

[figure not shown]
Study objectives	Study Endpoints
Primary objective	Primary Study Endpoints

 
To validate that in patients with symptomatic non-acute subdural hematoma (SDH), MMA embolization with liquid embolic materials can reduce a) the incidence of symptomatic hematoma
 
	
 
Incidence of symptomatic recurrence (in patients who undergo trepanation/drainage) or symptomatic progression of hematoma (in patients who do not undergo trepanation/drainage) within 90 days after randomization
 
Symptomatic hematoma recurrence is defined as maximum hematoma thickness >10 mm in patients in
 

Study objectives	Study Endpoints
recurrence for patients receiving trepanation and drainage and b) the incidence of symptomatic hematoma progression for patients undergoing conservative treatment.	
the trepanation group, combined with neurological symptoms, or that the patient needs to undergo re-operation
 
 
Symptomatic hematoma progression is defined as an increase of >3mm maximum thickness of SDH of patients in the non-trepanation group compared with baseline, or the need for surgery based on the assessment of the treating medical team
 

Secondary objectives	Secondary Study End Point

 
To validate the efficacy of MMA embolization with liquid embolic materials
 
	
 
Incidence of SDH symptomatic recurrence (in patients who undergo trepanation/drainage) and symptomatic progression (in patients who do not undergo trepanation/drainage) 360 days after randomization
 
Success rate of target vessel embolization in DSA imaging
 

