### 1.3. Study Design

#### Overview of Study Design and Key Characteristics

	
Design Features	
 
This is a multi-center, randomized, open-label, blinded evaluation endpoint, and parallel controlled clinical study. The study contents include: 1) Screening and baseline period: Confirm whether the patients are eligible for the study and make a record and decide whether trepanation and drainage should be performed by considering the condition of the disease and the imaging results, and then carry out randomization and therapy. Eligible subjects will be randomly assigned to the traditional treatment group or MMA embolization group at the ratio of 1:1. 2) Follow-up period: Assess patients for efficacy endpoints and safety endpoints at 30 days, 90 days and 360 days after randomization.
 

Study treatment	
 
MMA embolization: The surgery is performed under local anesthesia + analgesia, or general anesthesia, and the type of anesthesia is decided by the neurointerventionalists. Different types of catheters are chosen according to patients' anatomy. Arterial access is usually attained via femoral artery groin puncture, however radial or brachial artery access is also allowed. Angiography will usually show MMA dilatation and abnormal vascular staining on the affected side, and then embolic materials are slowly injected into the blood vessels, while avoiding reflux carefully. Investigators who use liquid embolic materials shall be qualified in corresponding training before they can perform the surgery.
 
Drug therapy: Drug treatment can be divided into the symptomatic treatment and treatment promoting hematoma absorption. Indications of drug treatment promoting hematoma absorption: 1) Confirmed diagnosis of non-acute SDH; 2) Patients complicated with multiple organ failure and coagulation dysfunction, etc. who are not suitable for surgery or refuse the surgery; and 3) To prevent postoperative recurrence after
 

Overview of Study Design and Key Characteristics	

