### **3. Sample Size Considerations**

The study hypothesizes that patients undergoing middle meningeal artery embolization may have lower symptomatic recurrence (in the trepanation/drainage group) and lower rates of symptomatic hematoma progression (in the non-surgical group) of subdural hematoma compared to patients who do not go MMA embolization. Two interim analyses will be conducted. With an expected symptomatic recurrence rate (trepanation/drainage group) / symptomatic progression rate (non-surgical group) after MMA embolization of 5% compared with 12% in the control group, and considering a loss to follow-up rate of 8%, a sample size of 722 cases with a two-sided alpha of 0.05 would yield 90% power.

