#### **4.2. Final Analysis**

The planned final analysis will be performed after the following steps are completed sequentially:

1. All subjects have completed the study as defined in the protocol.
2. The Statistical Analysis Plan (SAP) has been finalized and approved.
3. All required database cleaning is completed, and the head of Data Management department announces the final database release and database freeze.
4. Randomization codes are issued according to the unblinding process at the end of the trial.

Only blinded data will be reviewed prior to database lock. In addition, no database lock will occur prior to finalization of this SAP.

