**Table 4 Overview of planned primary efficacy endpoints analyses**

	Data Presentation Generated		
	Table	Figure	Listing
Incidence of recurrence (subjects with trepanation) or progression (subjects with no trepanation) of subdural hematoma within 90 days after randomization			
Number and percentage of subjects with event - Hematoma recurrence (in the trepanation/drainage group) in the MMA embolization and control arm respectively - Hematoma progression (in the non-surgical group) in the MMA embolization and control arm respectively - Death within 104 days (90 days + 14 days) in the MMA embolization and control arm respectively	Y		Y
Dichotomous data analyses:			Y

	Data Presentation Generated		
	Table	Figure	Listing

 
- Recurrence (in the trepanation/drainage group)/progression rate (in the non-surgical group) with 95% CI
 
- Difference in recurrence or progression rates between MMA embolization and control groups with 95% CI and CMH Chi-square P value
 
- OR and its 95% CI for the comparison of recurrence or progression rates between treatment and control groups
 
			

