## 8.2. Specifications of Primary Efficacy Endpoints Analyses

### 8.2.1. Definitions and Derivations

- **Symptomatic** SDH recurrence (in the trepanation/drainage group) refers to a situation in which the maximum thickness of hematoma of patients exceeds 10 mm, combined with neurological symptoms, or the need for repeat surgery.
- Symptomatic SDH progression (in the non-trepanation/drainage group) refers to a situation in which the maximum thickness of increases by more than 3 mm compared with baseline, combined with neurological symptoms, or the need for surgery.
- The results of central imaging evaluation and analysis of CT/MRI examinations required for the determination of the subject 's primary endpoint in this study will be presented in tables and listings, respectively. Central image evaluation will be performed by the independent Core Lab. Evaluation of neurological symptoms will be derived from the Outcome Assessment Committee (OAC) review data.
- It should be noted that if there is a record of reoperation in participants who have undergone trepanation/drainage, and there is a record of surgical treatment in subjects who have received medical therapy without trepanation/drainage, the occurrence of the primary endpoint can be directly determined, and hematoma thickness or neurological symptoms are no longer required.
- In case of non-negligible amounts of missing data (>5%), we will use the MCMC method based on the Missing at random (MAR) assumption to impute missing data. The regression model will include group, sex, age, BMI, baseline mRS score and baseline maximum

hematoma thickness. The number of imputations is 10, seed=1234, nbiter=200. SAS code examples for multiple imputation will be provided in Appendix 3.

- Hematoma recurrence (trepanation/drainage group) or symptomatic hematoma progression (non-surgical group) at day 90 will be analyzed as follows. If there is any discrepancy between EDC and central imaging assessment scan date in the determination of visit window, the date determined by central imaging assessment shall prevail.

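### The components of the 90-day primary endpoint have different time limits: deaths count to day 104 and late scans have no outer limit, while operations, read under the endpoint title, stop at day 90

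*SAP*

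**What the plan says.** **Endpoint window.** SAP 1.2 counts recurrence or progression "within 90 days after randomization", and the need for surgery is part of that definition. The Table 4 title agrees: "progression (subjects with no trepanation) of subdural hematoma within 90 days after randomization". Protocol 7.3.1 also uses 90 days. The Protocol writes post-procedure, but the note closing its section 2 counts follow-up from the day of randomization, so both documents share one time origin.

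**Operation.** Under SAP 8.2.1, if a reoperation (trepanation patients) or surgical treatment (medically treated patients) is on record, "the occurrence of the primary endpoint can be directly determined, and hematoma thickness or neurological symptoms are no longer required". The bullet gives no date, and Table 5 has no column for operations.

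**Death.** Under its 90-day title, Table 4 lists "Death within 104 days (90 days + 14 days) in the MMA embolization and control arm respectively". Table 5 and Appendix 3 repeat the 104-day limit for the primary analysis and both sensitivity analyses. The note in Protocol 7.3.1 counts death from any cause only to day 90. SAP 1.1 says Table 1 summarizes all changes to the planned analyses, and Table 1 has no entry for this one.

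**Scan.** The V4 window is day 90 ± 14. In the primary analysis, Table 5 uses a measurement taken outside that window as the 90-day result and states no latest day.

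**Timing and reuse.** The final analysis waits until "All subjects have completed the study as defined in the protocol", that is, through 360-day follow-up. SAP 9.1.2.1 carries the 8.2.1 definitions over to the secondary endpoints, including recurrence or progression at 360 days.

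**The concern.** A composite endpoint should ask the same question of every patient over the same period. Here the answer for days 91 to 104 depends on how the failure shows itself. The SAP extends death to day 104 and accepts scans to day 104 and beyond. It is silent on operations, which leaves them at the 90-day limit of the title.

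The gap has a further consequence. An operation between day 90 and the V4 scan can remove the hematoma that the scan would have measured. That patient is not an event by operation date and may not be one by scan, although treatment has plainly failed.

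At stake is who counts as an event in the primary analysis. Allocation is unblinded (Protocol 6.4), so this should not be left to whoever programs the derivation. The change to the death rule is also a departure from the Protocol that a reader of Table 1 would not find.

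**Working it through.** **1. The plan's own figure.** Inputs from SAP section 3: 12% v 5%, two-sided alpha 0.05, 90% power, 8% loss. Allocation is 1:1 (SAP 1.3). Pooled-variance formula without continuity correction:

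n per arm = [1.960·√(2·0.085·0.915) + 1.282·√(0.12·0.88 + 0.05·0.95)]² / 0.07² = 331.5, rounded up to 332.

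Total 2 × 332 = 664, and 664 / 0.92 = 721.7, rounded up to 722. The stated figure reproduces, and power at 332 per arm is 90.0%. The planning rates belong to a 90-day endpoint, so stating a day-90 cut-off leaves N at 722.

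**2. Time limits side by side (primary analysis).**

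| Component | Protocol | SAP |
|---|---|---|
| Endpoint title | 90 days (7.3.1) | 90 days (1.2, Table 4) |
| Operation | under the title: 90 days | no date in 8.2.1, no column in Table 5; under the title: 90 days |
| Death | 90 days (7.3.1 note) | 104 days (Tables 4 and 5, Appendix 3) |
| Scan and symptoms | V4, day 90 ± 14 | V4, days 76–104; out-of-window values also used, no outer limit (Table 5) |

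**3. The same day, three presentations.** Take day 97.

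- Death: event in the SAP, since 97 ≤ 104; non-event in the Protocol, since 97 > 90.
- V4 scan meeting the failure criteria: event, because day 97 lies within days 76–104.
- Operation: non-event, since 97 > 90. If the V4 scan follows on, say, day 102, it measures the hematoma after surgery.

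No planned sensitivity analysis shows the effect of the death rule, because all three rows of Table 5 use 104 days.

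**4. Size.** The planned rates imply 0.12 × 332 ≈ 40 and 0.05 × 332 ≈ 17 events. One reclassified patient moves an arm's rate by 1/332 = 0.30 points. The documents do not say when operations or deaths occur, so any effect on power rests on assumption. With 332 per arm:

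| Assumed events added after day 90 | Rates | Power |
|---|---|---|
| None | 12% v 5% | 90.0% |
| +1 point in each arm | 13% v 6% | about 87% |
| +2 points in each arm | 14% v 7% | 83.9% |
| +4 points in each arm | 16% v 9% | 78.0% |
| Control +1, embolization +2 | 13% v 7% | 73.2% |
| Constant hazard to day 104 | 13.7% v 5.8% | 93.6% |

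The last row uses 1 − 0.88^(104/90) = 0.137 and 1 − 0.95^(104/90) = 0.058. Power falls in some rows and rises in another, so the direction is not determined.

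**The case against.** The strongest reply is that the operation bullet is a rule of evidence, not of timing. It says what proof suffices for the primary endpoint, and that endpoint is already defined as within 90 days. An explicit exception for deaths suggests that components without one keep the default. Both arguments stand, and they rule out a reading that a reader might be tempted by: that the operation component has no limit, or a clock of its own, so that surgery up to day 360 enters the 90-day rate. SAP 4.2 shows only that later operations will be in the database at the final analysis, as in any trial with longer follow-up. Counting them would contradict the title and blur the separate 360-day endpoint. The documents state two limits, 90 and 104 days, together with an open-ended rule for late scans.

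The reply does not remove the inconsistency. Reading operations as stopping at day 90 is exactly what sets them against deaths at day 104 and scans beyond day 90. Nor does it explain why the death limit differs from the Protocol without an entry in Table 1.

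**Conclusion.** The primary endpoint applies inconsistent time limits to its components, and the death limit is an unlisted departure from the Protocol. Between days 91 and 104 a death or a scan-defined failure counts and an operation does not. A late scan can count with no stated end.

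This follows from the text, given that the operation rule inherits the title's 90 days. The possible loss of a case through surgery before the V4 scan is an inference from the visit window, not something the documents describe.

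A reader might also infer that late events dilute the treatment contrast and cost power, or that operation is the commonest component. The documents support neither: they give no timing of events and no breakdown by component, and the illustrative calculations run in both directions. What can be said is that a few patients may be reclassified, at about 0.3 points of an arm's rate each. This is worth correcting before database lock. It does not threaten the design or the sample size.

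**What to change.** Set one cut-off, counted from randomization, for both dated components (operation and death), and write it into SAP 8.2.1, Tables 4 and 5 and Appendix 3. Either choice is workable:

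- **Day 90** matches the endpoint title and the Protocol. The SAP should then also say how a patient operated on after day 90 but before the V4 scan is classified.
- **Day 104** for both closes that gap within the V4 window, but departs from the title and the Protocol. It must be listed in Table 1 with a reason.

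State the latest day on which an out-of-window scan may serve as the 90-day result, and treat anything later under the existing rule for missing 90-day data. Give the 360-day endpoint its own limits on the same principle: day 360, or day 390 if the V5 window of ± 30 days is used.

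The cost is a few sentences and date conditions in the derivation. A few events on days 91–104 will be reclassified. N stays at 722.

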3.1 Overall Study Design

This is a multicenter, phase III, prospective, randomized, open-label, and parallel controlled clinical study with blinded outcome assessment. Approximately 722 cases will be included in this study in China, with a ratio of 1:1 for randomization into the MMA embolization and

traditional treatment groups.

The study phases include: 1) Screening and baseline period: confirm whether patients are eligible for the study and create a record; decide whether trepanation and drainage should be performed by considering the condition of the disease and the imaging results; carry out randomized assignment and therapy. Eligible subjects will be randomly assigned to the traditional treatment group or MMA embolization group at a ratio of 1:1. 2) Follow-up period: visit patients for efficacy endpoints and safety endpoints at 30 days, 90 days, and 360 days post-procedure.

Figure 1. Schematic diagram of inclusion and randomization of subjects

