7.1.3 Estimation of sample size

This study hypothesizes that MMA embolization may reduce the recurrence (operation group) or progression (conservative treatment group) of SDH. The estimated recurrence or progression rate of hematoma in the MMA embolization group is 5%, while that of control group is 12%. When estimating bilateral 5% for the statistical significance level, 90% for power, and 8% for an acceptable rate of loss to follow-up, the total sample size is estimated to be 722 cases.

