#### **SAS Code Sample:**

```
proc mi data=im1 seed=1234 n impute=20 out=im2
round=....1
min=....0
max=....1;
;
by trtan;
var sex age bmi basemrs basemth aval;
mcmc chain=multiple nbiter=200 niter=100;
run;
```

```
proc sort data=im2;
```

```
by _imputation_ trtan usubjid siteid;
run;
```

```
proc transpose data=im2 out=im2_t(rename=(_name_=avisit coll=aval));
```

```
by _imputation_ trtan usubjid siteid;  
var v1 v2;  
run;
```

```
proc sql noprint;  
create table im2_count as  
select distinct  
    _imputation_,  
    trtan,  
    avisit,  
    aval,  
    count(*) as count  
from im2_t  
group by _imputation_,trtan,avisit,aval  
order by _imputation_,trtan,avisit,aval  
;  
quit;
```

```
/*clopper-pearsen 95%ci*/  
ods select none;  
proc freq data= im2_count;  
    by _imputation_ trtan avisit;  
    table aval / binomial (cl=exact) alpha=0.05;  
    weight count;
```

```
ods output binomial=binomial;
```

```
run;
```

```
ods select all;
```

```
proc transpose data=binomial out=binomial_t;
```

```
by _imputation_ trtan avisit;
```

```
var nvalue1;
```

```
id label1;
```

```
quit;
```

```
proc sort data=binomial_t;
```

```
by trtan avisit _imputation_;
```

```
run;
```

```
ods select none;
```

```
proc mianalyze data=binomial_t;
```

```
by trtan avisit;
```

```
modeleffects proportion;
```

```
stderr ase;
```

```
ods output parameterestimates=binomial_t_pool;
```

```
run;
```

```
ods select all;
```

```
/*mn*/
```

```
proc freq data=im2_t;  
  by _imputation_ ;  
  tables trtan *aval / commonriskdiff (cl=score test=score) riskdiff (cl=mn);  
  ods output commonpdifftests=commonpdifftests1 commonpdifff=commonpdiffl  
    pdiffcls=pdiffcls1 riskdiffcol1=riskdiffcol11;  
run;
```

```
data riskdiffcol11;  
set riskdiffcol11(where=(row="difference"));  
run;  
proc sort data=riskdiffcol11;  
  by _imputation_ ;  
run;
```

```
proc mianalyze data=riskdiffcol11;  
  modeleffects risk;  
  stderr ase;  
  ods output parameterestimates=pest1_pool;  
run;
```

```
/*cmh*/
```

```
*** perform cmh test;  
proc freq data=im2_t;
```

```
tables strata*trtan*aval/cmh;  
ods output cmh=cmh;  
by _imputation_;  
run;  
*** apply wilson-hilferty transformation to the cmh statistic and  
standardize the resulting normal variable;
```

```
data cmh_wh;  
set cmh(where=(alhypothesis="general association"));  
cmh_value_wh=((value/df)**(1/3) - (1-2/(9*df))/sqrt(2/(9*df));  
cmh_sterr_wh = 1.0;  
run;
```

```
*** combine results;  

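### Above 5% missing, the primary imputation ignores that unseen patients have no recorded operation or death, so event rates may be overstated and the arm difference biased, modestly at the planned loss

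*SAP*

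**What the plan says.** SAP 8.2.1 and Table 5 (repeated in Appendix 3) set four rules for the primary analysis.

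- **Operations.** Where a reoperation (surgical stratum) or an operation (non-surgical stratum) is on record, "the occurrence of the primary endpoint can be directly determined, and hematoma thickness or neurological symptoms are no longer required".
- **Deaths.** Death up to day 104 is an event in every analysis.
- **Out-of-window visits.** The measurement is used as the 90-day result, so these patients are not imputed.
- **No 90-day data.** If more than 5% of outcomes are missing, the composite is multiply imputed under missing at random. Below 5%, missing counts as no event.

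On the imputation model the text says "The regression model will include group, sex, age, BMI, baseline mRS score and baseline maximum" hematoma thickness. The Appendix 3 code runs PROC MI separately by arm with "var sex age bmi basemrs basemth aval", where the last variable is the composite outcome. Neither place uses last contact, operation status, vital status or surgical stratum.

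On loss, SAP section 3 has "considering a loss to follow-up rate of 8" per cent. On capture, the note closing Protocol section 2 says that endpoint and safety events are collected at the follow-up visits. Protocol 7.1.4 says that missing values are not imputed; I take the later SAP as operative.

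**The concern.** Two rules in the same SAP section do not fit together. One makes operated and deceased patients observed whether or not they attend at day 90. The other imputes everybody else from a model fitted to all observed patients of the arm, those operated and deceased patients included. A patient who reaches the imputation step is known to have escaped both event types up to last contact, and the model does not use this. Whether an outcome is observed then depends partly on the outcome itself, which the stated missing-at-random assumption, given only arm and baseline covariates, does not allow.

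What is at stake is the primary estimate. If visit loss reaches the planned 8% by day 90, the 5% trigger would probably be passed and this would be the primary analysis. The imputed risk would be too high in each arm. The excess in points is larger in the arm with more operations and deaths, or with more unseen patients.

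**Working it through.** **Plan's own figure.** Protocol 7.1.3: "The estimated recurrence or progression rate of hematoma in the MMA embolization group is 5%, while that of control group is 12" (per cent). With a two-sided 5% level, 90% power and 8% loss, it arrives at 722 patients. The pooled-variance formula for two proportions without continuity correction gives 332 per arm. 332 / 0.92 = 360.9, so 361 per arm and 722 in total, which reproduces.

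**Inputs.** From the documents: p = 0.12 (control) and 0.05 (embolization), a true difference of 7.00 points; m = 0.08 as the share without a usable visit. Not in the documents, so assumed and varied:

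- s, the share of events that are operations or deaths;
- c, the share of those still recorded in patients without a visit;
- m by arm.

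Visit loss is taken as independent of the outcome, and baseline covariates as weak predictors, so the imputed risk equals the observed same-arm rate. The rounding and bounds in the Appendix 3 code are a separate matter and are left out.

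**Formulas, per arm.** Let k = m·s·p·c, the patients without a visit whose operation or death is recorded.

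- Observed (and imputed) rate: r = [p(1 − m) + k] / [(1 − m) + k]
- True risk in those imputed: q = p(1 − sc) / (1 − spc)
- Share imputed: m(1 − spc)

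**Example: m = 0.08, s = 0.5, c = 1.**

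- Control: k = 0.0048; r = 0.1152 / 0.9248 = 12.46%; q = 0.06 / 0.94 = 6.4%
- Embolization: k = 0.002; r = 0.048 / 0.922 = 5.21%; q = 0.025 / 0.975 = 2.6%
- Difference: 7.25 points. Excess imputed events are about 1.7 and 0.7 per 361.

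At s = 1: r = 0.12 / 0.9296 = 12.91% and 0.05 / 0.924 = 5.41%. The difference is 7.50, with about 3.3 and 1.5 excess events.

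**Expected difference in points (true value 7.00), 8% unseen in each arm:**

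| Capture c | s = 0.5 | s = 0.75 | s = 1 |
|---|---|---|---|
| 1 | 7.25 | 7.37 | 7.50 |
| 0.5 | 7.13 | 7.19 | 7.25 |
| 0 | 7.00 | 7.00 | 7.00 |

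**Unequal missingness, c = 1, s = 0.5 to 1:**

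- 4% control / 12% embolization unseen: 6.90 to 6.79
- 12% control / 4% embolization unseen: 7.62 to 8.22
- Equal true rates of 5-12% with 4% / 12% unseen: a spurious difference of 0.2 to 1.0 points, its sign set by which arm has more unseen

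**Odds ratio.** The formula for r gives r/(1 − r) = [p/(1 − p)] × [1 + smc/(1 − m)]. With the same s, m and c in both arms the factor cancels, and the odds ratio stays at (0.12/0.88) / (0.05/0.95) = 2.59. Under those conditions only the absolute difference moves.

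**The case against.** A reader might infer that missing at random fails by construction and that the difference is inflated whenever embolization works. The documents do not support either statement.

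- **Capture.** Endpoint events are collected at visits, so no recorded operation is not the same as no operation. If nothing is captured in patients without a visit, the planned imputation is unbiased on this account. But zero capture is unlikely. Protocol 6.5 records SAEs, deaths and re-hospitalizations at days 30, 90 and 360, and the SAE definition in Protocol 10.2 covers hospitalization and operative intervention. Events before day 30 are thus known for anyone seen then, and a patient who returns at day 360 can supply earlier ones.
- **Direction.** Overstatement of the difference needs similar missingness by arm. The documents give none by arm, treatment is open-label, and the bias reverses in the 4% / 12% case.
- **Trigger.** The 8% is an allowance for loss to follow-up and is not tied to day 90 in a trial that runs to day 360. Captured events and out-of-window scans reduce endpoint missingness further. At 5% visit loss with full capture and s = 1, only 4.4% and 4.75% would be missing, and imputation would not run.
- **Size.** The largest excess at 8% equal loss is 0.50 points, against a standard error of √(0.12·0.88/361 + 0.05·0.95/361) = 2.1 points, or about a quarter of one standard error.
- **Existing sensitivity analysis.** Sensitivity Analysis 2 counts patients without 90-day data as no event, the opposite extreme. It does not isolate this problem, because it also recodes out-of-window visits as no event and sets the risk in unseen patients to zero. In general the risk lies between zero and the imputed rate.

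The first four points limit the concern and stand. None supplies the missing conditioning.

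**Conclusion.** The point holds in a limited form. As written, the imputation ignores known freedom from recorded operation and death up to last contact, and it may overstate event rates to the extent that such events are captured in unseen patients. With similar missingness by arm and a true benefit, the absolute difference may be modestly overstated, by 0 to 0.50 points on 7.00 at 8% unseen, depending on capture and on the operation/death share. With unequal missingness the bias can go either way, and it need not be zero when there is no treatment effect. All of this applies only if more than 5% of primary outcomes are missing, which is likely at the planned loss but not assured. The operation/death share, the capture and the missingness by arm are assumptions. The plan should be changed because this may be the primary analysis and the data needed are already collected, not because the trial's conclusion is likely to turn on it.

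**What to change.** In SAP 8.2.1 and Appendix 3, state that each unseen patient is imputed from patients of the same arm and surgical stratum who had no recorded operation or death up to that patient's last contact. Donors' later operations and deaths stay in as events. A workable form is separate imputation by last attended visit (discharge or day 30), within arm and stratum.

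Impute only the scan-plus-symptom component, from patients with neither operation nor death, solely where operation status is known for the whole 90 days and vital status to day 104. With full capture this returns the expected difference to 7.00 points.

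Do not restrict PROC MI, as a general rule, to all patients without a recorded operation or death. That assumes no operation after last contact. With none captured, the arm estimate becomes p(1 − m) + m(1 − s)p/(1 − sp). At 8% unseen this gives differences of 6.75, 6.60 and 6.51 points for s = 0.5, 0.75 and 0.9, an error about as large as the one to be removed.

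The cost is somewhat more programming and possibly small donor sets in some arm-by-stratum-by-visit cells. No new data are needed: operation, death and visit dates are already collected.
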